Clinical assessments and sample collection will occur at regularly scheduled visits through Week 48 with telephone follow-up conducted in the interim. If a subject has not recovered B cells by Week 48, B cell studies will be conducted quarterly until recovery is documented or for 2 years after initial treatment (whichever occurs first). Recovery is defined as the time point at which B cells recover to within 10% of baseline levels; if a baseline value is not available then recovery is defined as a B cell level of at least 90% of the lower limit of

normal. During this quarterly monitoring period of B cell recovery, AEs and SAEs will be assessed, providing the subject has not withdrawn consent, to capture any infectious event \geq Grade 3 using the National Cancer Institute - Common Terminology Criteria for Adverse Events (NCI-CTCAE). No additional study-related data will be collected. Vital status on all subjects will be evaluated \geq 2 years after randomization.

The primary efficacy endpoint is the change in 6MWD from baseline to 24 weeks after treatment initiation. Hemodynamic measures will be assessed at baseline and Week 24, contributing to the understanding of the relationship between PVR and clinical endpoints. Initiation of new PAH therapy due to disease worsening prior to Week 24 will prompt an endpoint visit and right heart catheterization prior to initiation of the new therapy. B cell recovery for all will be monitored by serial assessments of B cell counts as determined by flow cytometry.

The total duration of the study is anticipated to be approximately 8 years.

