3.3.3 Subject Withdrawal from the Study

When a subject is withdrawn from the study after initiating treatment but prior to B cell follow-up, protocol-specified treatment requirements are discontinued and study-related visits, exams, procedures, assessments, tests and data collection are terminated after completion of an Early Endpoint Visit as detailed in Section 6.5.5, *Early Endpoint Visit*. However, individual subjects will be withdrawn from the protocol under the following conditions:

1. The subject withdraws consent.
2. The investigator or DAIT/NIAID believes it is in the best interest of the subject.
3. The study is terminated.

Subjects who are lost to follow-up will also be regarded as withdrawn from the protocol.

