6.5.4.13 Week 104 (Visit 17)

An assessment of vital status approximately two years post randomization will be conducted via telephone or review of public records or health registries (to which the subject has consented to share this data).

For subjects who completed their participation prior to the approval of protocol version 8.0, every possible effort to contact these subjects to consent them for this assessment should be made.

Assessments:

- Vital status
- Treatment Satisfaction assessment

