- ²¹ TB testing (PPD or QuantiFERON®-TB Gold In-Tube Test [QFT-G_IT]): unless performed within 30 days prior to screening and documented as negative in the subject's records or unless subject is known to have a positive test and has documentation of appropriate therapy.
- ²² If the Screening physical exam, oxygen saturation, and chemistry panel are performed within 7 days of Day 0, they do not need to be repeated during the Randomization/Baseline or Day 0 visits unless clinically indicated.
- ²³ Only infectious events ≥ NCI-CTCAE grade 3 will be reported.
- ²⁴ Required only if the unscheduled visit is due to an increase in SSc-PAH disease activity; see Section 6.5.8, *Unscheduled Visit* for further details.
- ²⁵ Hemoglobin, platelets, lymphocytes, neutrophils, and bands results from a hematology specimen drawn within 24 hours of the infusion must be reviewed prior to initiating the study drug infusion (see Section 5.3.6, *Criteria for Withholding Rituximab Infusion*).
- ²⁶ A member of the research staff will obtain verbal consent to conduct an assessment of vital status and treatment satisfaction approximately two years post randomization for each subject. If the subject cannot be reached, a review of public records or health registries should be completed.

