- f. Worsening of 6MWD by > 20% and an increase in functional class: The 6MWD and the NYHA Functional Class Assessment will be performed at Screening and Weeks 4, 12, 24, 36, and 48; they may also be performed at an unscheduled visit. Data for the 6MWD will be collected on the 6-Minute Walk Test CRF page and data on functional class will be collected on the NYHA Functional Class Assessment CRF. The first date at which the 6MWD has decreased by >20% from the Screening walk distance and the NYHA Functional Class Assessment has increased a class from Screening will be recorded. If a subject’s 6MWD decreased from Screening by more than 20% and a repeat 6MWD was performed, then the better of the two values will be used in the analysis. If a subject is NYHA Class IV at baseline, then only a decrease of 20% in the 6MWD will be required.

Time to clinical worsening will be defined as the first date that meets any of the above criteria and will be calculated in study days as: date of first event – date of randomization. If a subject does not experience a relevant event by Week 48 or if the date of death is after the 48 week follow-up period, then time to clinical worsening will equal the duration of follow-up in the main study for that subject. Appropriate censor variables will be defined to indicate whether the time-to variable represents an event time or a censor time.

Analysis: Time to clinical worsening and type of clinical worsening reached will be summarized by treatment group and overall. Kaplan-Meier curves, including 95% confidence intervals, will be created for each treatment arm and will be compared using the log-rank test. A Cox proportional hazards model may be fit to assess the effect of treatment on time to clinical worsening, if appropriate. Additional covariates may be added to the model as appropriate. Analyses will be run using the definition of hospitalization of SSc-PAH as defined in both point B and B.i above.

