8.3.2. Deaths

Any death that occurs while a subject is active in the main study (up to Week 48) will be collected and reported as a SAE, and any death that occurs after main study completion will only be reported as a SAE if the subject is active in quarterly monitoring for B cells and if the cause of death is determined to be a Grade 3 or higher infection. Additionally, an assessment of vital status approximately two years post randomization will be conducted via telephone or

review of public records or health registries (to which the subject has consented to share this data). Any deaths discovered from this review will be recorded on the Post-Study Follow-Up/ Week 104 Vital Status CRF page.

Treatment-related mortality will be defined as death occurring after randomization and before Week 48, and possibly, probably, or definitely resulting from study treatment. Treatment-related mortality can only be assessed if a death was reported as a SAE; relationship to study treatment was not collected for deaths recorded on the Post-Study Follow-Up/ Week 104 Vital Status CRF page. As such, treatment-related mortality will be summarized at Week 48.

All-cause mortality, defined as any death occurring after randomization, will be summarized at Week 48 and Week 104.

In addition, time to all-cause mortality will be defined as the number of months post-randomization until death from any cause. If death does not occur during the post-randomization study period (up to Week 104), then time to all-cause mortality will be set equal to Week 104 or the day of the Week 104 vital status telephone call, whichever occurred first. Appropriate censor variables will be defined to indicate whether the time-to variables represent event times or a censor times. Kaplan-Meier survival curves from each treatment arm will be compared using the log-rank test.

Separate displays listing and summarizing death, including time to death and cause of death, will also be created

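### SAP 8.3.2 carries every subject without a death to Week 104 (or an earlier call date), including any of unknown vital status, so undetected deaths would inflate two-year survival

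*SAP*

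**What the plan says.** SAP 8.3.2 defines time to all-cause mortality from randomization. If no death occurs by Week 104, "time to all-cause mortality will be set equal to Week 104 or the day of the Week 104 vital status telephone call", whichever comes first. Kaplan-Meier curves by arm are then compared with a log-rank test. The same section adds a proportion-type summary: "All-cause mortality, defined as any death occurring after randomization, will be summarized at Week 48 and Week 104". Neither sentence mentions a subject whose status at Week 104 is not known.

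The protocol intends complete ascertainment. Section 3.1 states "Vital status on all subjects will be evaluated" at two years or later after randomization, and Table 6.1, note 26 adds a fallback: "If the subject cannot be reached, a review of public records or health registries should be completed".

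Other passages leave room for unresolved subjects:

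- Protocol 6.5.4.13 says of subjects who finished before version 8.0 that "every possible effort to contact these subjects to consent them for this assessment should be made". It limits at least part of the record route to "health registries (to which the subject has consented to share this data").
- Protocol 3.3.3 says "Subjects who are lost to follow-up will also be regarded as withdrawn from the protocol", and study data collection ends on withdrawal.
- By SAP 8.3.2, a death after main-study completion becomes an SAE only if the subject is in B-cell monitoring and the cause is a Grade 3 or higher infection. The two-year check is therefore the main source of late deaths.

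For time to clinical worsening (SAP 7.3.3), a subject without an event is treated differently: "time to clinical worsening will equal the duration of follow-up in the main study for that subject".

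**The concern.** Censoring at Week 104 asserts that the subject was observed alive and at risk until then. For a subject of unknown status nothing supports that. The rule gives the least-known subjects the longest event-free follow-up: someone reached alive shortly before Week 104 is censored on the day of the call, while someone never traced is credited with the full period.

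If any of the untraced subjects died, they stay in the risk set and their deaths are not counted. Two-year survival is then too high and the Week 104 mortality proportion too low. All-cause mortality is a named safety endpoint (protocol 3.2.3), and the two-year curve by arm will be read in a disease with high mortality. The SAP does not require a count of unknown status, so a reader could not judge how far to trust that curve.

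**Working it through.** The documents state no two-year mortality estimate or power figure for this trial, so there is no plan figure to reproduce.

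**Step 1: who receives which time under SAP 8.3.2**

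| Subject without a recorded death | Time assigned | Supported? |
|---|---|---|
| Alive at a call before Week 104 | Call date | Yes |
| Alive at a call at or after Week 104 | Week 104 | Yes |
| Not reached; completed search to Week 104 finds no death | Week 104 | Yes |
| Neither reached nor covered by a completed search | Week 104 (no call date exists) | No |

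**Step 2: one arm of 30** (arm size from the protocol synopsis). With no earlier censoring, each undetected death adds 1/30 = 3.3 points to reported survival. An unresolved subject who is alive adds nothing. Illustration with 9 known deaths and 3 unresolved subjects last seen before any death:

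- Current rule: 21/30 = 70.0%, correct if all 3 are alive.
- Censoring at last contact: 18/27 = 66.7%.
- Truth if all 3 had died: 18/30 = 60.0%.

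**Step 3: expected overstatement.** Let u be the share of subjects assigned a loss time and never resolved, with loss unrelated to death and none of their later deaths found. Then

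excess = u × [P(death by Week 104) − P(death before loss)].

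Assumed exponential survival at Week 104 is 63%, 80% or 90%. The 63% is the protocol's background two-year figure (section 1.1), measured from diagnosis rather than randomization, so all three are assumptions. At 63%:

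- Loss uniform over Weeks 0-48: u × (0.370 − 0.099), or 0.27 points per 1% unresolved.
- Loss at Week 48: u × (0.370 − 0.192), or 0.18 points per 1%.

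| True survival | Points per 1%, uniform loss | Points per 1%, loss at Week 48 | Reported with 10% lost, uniform |
|---|---|---|---|
| 63% | 0.27 | 0.18 | 65.7% |
| 80% | 0.15 | 0.10 | 81.5% |
| 90% | 0.08 | 0.05 | 90.8% |

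If u counts only subjects alive at last contact, the figures per 1% are 0.30, 0.16 and 0.08 (uniform) and 0.22, 0.11 and 0.06 (Week 48).

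A separate check used a piecewise exponential curve through the protocol's 81% at one year and 63% at two. It gives 63 + 10% × (90.7 − 63) = 65.8% for last contact at Week 24, and 63 + 10% × (82.3 − 63) = 64.9% for Week 48. Censoring at last contact returned 62.8% to 63.2% in simulation.

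**Step 4: if some later deaths are found while survivors stay unresolved.** Simulation of 400,000 subjects per setting, 10% lost uniformly over Weeks 0-48, true survival 63%:

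| Later deaths found | Current rule | Censor at last known alive |
|---|---|---|
| 0% | 65.7% | 63.2% |
| 50% | 64.4% | 62.0% |
| 80% | 63.6% | 61.4% |

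**Step 5: log-rank type I error under the current rule.** 30 per arm, equal true mortality, no record resolution, 10,000 simulated trials per setting, Monte Carlo error about 0.2 points (0.3 at the largest value):

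| Lost, arm A vs arm B | 63% | 80% | 90% |
|---|---|---|---|
| No loss | 5.3% | 4.9% | 5.5% |
| 5% vs 15% | 5.5% | 5.4% | 5.1% |
| 5% vs 20% | 6.2% | 5.4% | 5.2% |
| 5% vs 35% | 9.8% | 7.7% | 5.8% |

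**The case against.** The case for leaving the text alone has four parts.

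- **The rule speaks of subjects in whom death does not occur, and is merely silent on unknown status.** SAP 8.1 rules out imputing missing safety data, and 8.3.2 leaves the censor indicators to be defined, so a programmer could treat unknowns differently. Neither passage supplies another time, however. On the stricter reading, unresolved subjects have no defined time at all, which also needs repair.
- **Ascertainment is planned for everyone, with records as a fallback, so there may be nobody unresolved.** This stands, and the size of the problem cannot be fixed from the documents. It does not say what happens when both routes fail.
- **The contrast with clinical worsening is imperfect.** That endpoint includes walk distance and functional class, which need visits, whereas death can be found without contact. This stands: 7.3.3 shows that the SAP can end time at actual follow-up, but not that the two rules must match.
- **Censoring may be no better.** Step 4 shows that if more than roughly 50-60% of later deaths are found while survivors stay unresolved, the current rule is nearer the truth. The arithmetic is right. That situation requires survivors to remain unresolved after a search, and the change proposed here counts a completed search with no death found as resolved. The risk is reduced, not removed, and it justifies keeping the current rule as a sensitivity analysis.

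**Conclusion.** The concern holds. As written, SAP 8.3.2 treats a subject of unknown status as alive to Week 104. The direction of any error is known: survival too high and mortality too low. Its size depends on three quantities the documents do not give, namely the share unresolved after both routes, when they were last seen, and how many of them died. With 10% unresolved, the assumptions of Step 3 give an overstatement of 0.5 to 2.7 points. With nobody unresolved, or all of them alive, it is zero.

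The comparison between arms is hardly touched unless loss is very unequal. Protocol 8.3.1 makes safety comparisons exploratory, and the primary endpoint is unaffected. The consequence is confined to the reported two-year survival and mortality by arm, so the change is worth making but not critical.

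**What to change.** Amend SAP 8.3.2 as follows:

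1. Keep Week 104, or the call date if earlier, for subjects confirmed alive by the call or covered by a completed record or registry search through that date with no death found.
2. Censor subjects resolved by neither route at the last date known alive, no later than Week 104.
3. Report the number with unknown Week 104 status by arm, beside both the survival curve and the Week 104 mortality proportion.
4. State that this censoring assumes loss and ascertainment are unrelated to death, and present the all-alive result (the current rule) as a sensitivity analysis.

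The cost is two or three sentences, a last-known-alive date derived from data already held, and a flag for a completed search. SAP 5.1 already tabulates reasons for early termination, which covers part of the reporting. Late confidence intervals will be slightly wider, and survival may be somewhat understated if deaths among lost subjects are traced more readily than survivors. If every subject is resolved, the estimate does not change and the report can say that follow-up was complete.

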8.4. Clinical Laboratory Evaluation

Clinical laboratory measurements include serum chemistry and hematology. Subjects randomized prior to March 19, 2013 had serum chemistry and hematology results analyzed by their sites local lab. Data for these labs is collected on the Hematology and Chemistry CRF pages. Subjects randomized after March 19, 2013 have serum chemistry and hematology labs run by the central lab, ICON. Results will be converted to standardized units where possible.

For numeric laboratory results, descriptive statistics of laboratory values and the change from baseline of laboratory values will be presented for each treatment group and overall. For categorical laboratory results, the number and percentage of subjects reporting each result will be presented for each treatment group and overall.

Laboratory data will be plotted to show patterns over time. Summary statistics including 25th percentile, median, and 75th percentile will be plotted for each visit by treatment group. Lines connecting individual subject results from subjects with grade 2 or higher values will be overlaid on each figure. For lab results that are not gradable, results from subjects with values outside of 2 *upper limit of normal or 0.5*lower limit of normal will be overlaid. Tests with qualitative results (such as “present” or “positive”) will not be plotted. Reference ranges from the central lab will be used.

In addition, abnormal and clinically significant abnormalities will be summarized and listed separately.

8.5. Vital Signs, Physical Findings, and Other Observations Related to Safety

8.5.1. Vital Signs

Descriptive statistics of vital signs results and change from baseline of vital signs will be summarized for each treatment group and overall. Data listings sorted by treatment group, subject, vital sign parameter, and time of assessment will be provided for vital signs measurements. Data will be plotted to show patterns over time. Summary statistics including 25th percentile, median, and 75th percentile will be plotted for each visit by treatment group.

8.5.2. Physical Examinations

Data listings will be provided for physical examination results and sorted by treatment group, subject, body system, and time of assessment.

9. OTHER ANALYSES

9.1. Use of Medications

9.1.1. Prior and Concomitant Medications

Medications will be coded according to the World Health Organization (WHO) Drug Dictionary (version 2010.03). Medications reported on the Prior/Concomitant Medications CRF will be categorized for analysis as prior or after study treatment by comparing the medication start and stop dates with the first and last dose of study medication dates. Prior medications will have both the medication start and stop dates prior to the first dose of study medication date. Concomitant medications will have a medication start date on or after the first dose of study medication. Medications taken for the treatment of PAH will be summarized separately, see Section 9.1.2 below.

The number and percentage of subjects receiving prior and concomitant medications will be presented overall and by medication class. When reporting the number of subjects receiving the medication, a subject will only be counted once if they ever received the medication within the medication class. Percentages will be based on the number of subjects in the analysis population.

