5.7.2 Immunosuppressive or Immunomodulating Drug Treatment

Concurrent therapy with non-biologic immunosuppressive or immunomodulating drugs (including, but not limited to, methotrexate, hydroxychloroquine, penicillamine, mycophenolate, azathioprine or cyclosporine) is permitted. Doses must remain stable for at least the four weeks prior to randomization through at least the 24 week primary endpoint visit unless adjustment is needed for the management of toxicity.

Doses of concurrent non-biologic immunosuppressive or immunomodulating drugs may be increased or new non-biologic immunosuppressive or immunomodulating drugs may be initiated for worsening SSc disease manifestations after the week 24 endpoint visit.

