8.5 Other Statistical Considerations

8.5.1 Covariates

The primary analysis will be adjusted for as stated above.

If the analyses described in Section 8.5.4, *Examination of Subgroups* yield covariates that differ significantly between treatment groups, then, as a secondary analysis, these covariates may also be considered for adjustment in the models specified for the primary analysis.

Covariates that may be considered include, but are not limited to: age, study center, gender, race, duration of SSc-PAH disease, baseline and concomitant medication use, undergoing cardiopulmonary rehabilitation (yes/no), non-biologic immunosuppressive or immunomodulating drug use (yes/no), and non-biologic immunosuppressive or immunomodulating drug change after 6 months (yes/no).

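### SAP 9.1.1 leaves non-PAH drugs that were started before the first dose and continued past it out of both the prior and the concomitant medication tables

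*SAP*

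**What the plan says.** SAP 9.1.1 takes the records on the Prior/Concomitant Medications CRF, which "will be categorized for analysis as prior or after study treatment by comparing the medication start and stop dates"; the reference dates are those of the first and last study dose. Two rules follow. The first sets the earlier class: "Prior medications will have both the medication start and stop dates prior to the first dose of study medication date".

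The second sets the later class and looks at one date only: "Concomitant medications will have a medication start date on or after the first dose of study medication".

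The output is limited to these two classes: "The number and percentage of subjects receiving prior and concomitant medications will be presented overall and by medication class". PAH drugs are handled elsewhere: "Medications taken for the treatment of PAH will be summarized separately, see Section 9.1.2 below".

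On the drugs at issue, Protocol 5.7.2 permits "Concurrent therapy with non-biologic immunosuppressive or immunomodulating drugs" and adds: "Doses must remain stable for at least the four weeks prior to randomization through at least the 24 week primary endpoint visit", with an exception for managing toxicity. Protocol 5.7.2.1 permits prednisone, or an equivalent, at up to 10 mg daily. Protocol 8.5.1 names "baseline and concomitant medication use" and, separately, use of non-biologic immunosuppressive or immunomodulating drugs among the covariates that may be considered in secondary analyses.

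**The concern.** The two rules do not cover every possible pair of dates. The pair they miss, a start before the first dose with use continuing past it, is the usual pattern for stable background therapy. Under Protocol 5.6, a new non-biologic immunosuppressant before Week 24 is prohibited except to manage toxicity. Up to Week 24, the concomitant table would therefore show mainly exceptions and deviations for that class and omit the permitted background use.

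What is at stake is interpretation. Protocol 1.4 notes that the effect of rituximab on infection is hard to judge when patients are also taking immunosuppressive drugs, and infection-related events are a safety endpoint (Protocol 3.2.3). The adaptive randomization balances site, baseline PVR and time since diagnosis (Protocol 3.1.1), not immunosuppression, so with 30 subjects per arm a chance imbalance is possible. SAP 7.2.3 item 5 allows adjustment for baseline characteristics that differ meaningfully between arms, but an imbalance that no table displays is easy to overlook.

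**Working it through.** The plan states no figure on this point, so the check is one of logic. Set day 0 as the date of first dose, s as the start day and e as the stop day.

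- Prior: s < 0 and e < 0.
- Concomitant: s ≥ 0.
- Neither: s < 0 and (e ≥ 0 or ongoing).

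Examples:

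| Start day | Stop day | Class under SAP 9.1.1 |
|---|---|---|
| -60 | -10 | prior |
| -1 | 0 | neither |
| -60 | 56 | neither |
| -200 | ongoing | neither |
| 0 | 0 | concomitant |
| 30 | ongoing | concomitant |

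To confirm that nothing else is missed, take every start day from -30 to +30, with every stop day from the start day to +30 plus ongoing.

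- Each start day has (30 − s + 1) + 1 = 32 − s possible stops. Summed over 61 start days this is 61 × 32 − 0 = 1952 patterns.
- Prior: 1 + 2 + … + 30 = 465.
- Concomitant: 31 × 32 − 465 = 527.
- Neither: 30 start days × 32 stops (days 0 to 30, plus ongoing) = 960.
- Total: 465 + 527 + 960 = 1952.

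The 960 unclassified patterns are exactly those that span the first dose. The ratio 960/1952 depends on the grid chosen and does not estimate the share of real records or subjects.

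Next, do permitted background drugs fall in that group? A non-biologic immunosuppressant that complies with Protocol 5.7.2 was at a stable dose at least four weeks before randomization and continues to at least Week 24 unless toxicity intervenes. It therefore has s < 0 and e > 0, which is neither class. Prednisone is less tightly fixed. It must not change in the four weeks before randomization (Protocol 4.2, criterion 6), may then move within 0 to 10 mg, and must be stable for the four weeks before Weeks 24 and 48 (Protocol 5.7.2.1). A course that began before the first dose and ran past it is still unclassified.

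Last, does another planned display show this use?

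- SAP 9.1.2 covers PAH drugs only.
- SAP 5.2 lists the number of PAH medications among baseline characteristics, but not immunosuppressant or steroid use.
- SAP 6.2 lists concomitant therapy during study drug administration by subject and infusion visit, with no count or percentage by arm.
- SAP section 11 records no change on this point.

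**The case against.** The best defence is that this is a drafting slip in a descriptive section. The SAP mentions the last-dose date and then uses it in neither rule, which suggests an unfinished sentence; a programmer would probably apply the usual definition anyway. The data are not lost, because concomitant medications are recorded at screening and at each scheduled visit through Week 48. The covariates in Protocol 8.5.1 can be derived directly from the recorded dates and are optional. The primary model in SAP 7.2.2 has no medication term, and the sensitivity analysis for changed PAH therapy draws on a different CRF page.

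Most of that stands, and it limits the consequence. It does not remove the gap: silently applying another definition would depart from an explicit rule in the plan.

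The following stronger readings are tempting, but the documents do not support them:

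- That the tables would show almost no immunosuppressant or steroid use. Drugs started on or after the first dose are still counted. These include short steroid courses allowed by Protocol 5.7.2.1, immunosuppressants started after Week 24, and possibly the Week 2 premedication if it is entered on this CRF, which is not stated.
- That every subject on background therapy disappears. If sites enter a dose change as a new record with a new start date, that record would count as concomitant. The entry rule is not given.
- That balance between arms could not be examined at all. It could be, from the raw dates.
- That immunosuppression is the leading modifier of the treatment effect. Protocol 8.5.1 lists it as one candidate among several, and it is not a named subgroup in Protocol 8.5.4 or SAP 7.4.

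**Conclusion.** The point holds as a gap in the definitions. Applied as written, SAP 9.1.1 leaves every non-PAH record that spans the first dose out of both tables, and no other planned summary shows that use by arm. The concomitant table would therefore under-count carried-over co-treatment. The number of subjects affected cannot be worked out, because the documents do not say how many enter on such drugs or how dose changes are recorded.

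The consequence is limited to the descriptive account of co-treatment, which helps in reading infection events and in noticing imbalance in candidate covariates. A reader might infer that the efficacy results are at risk. They are not: no efficacy estimate, test or error rate depends on this classification. The conclusion assumes that the two rules are applied literally and that background immunosuppressants and steroids are recorded on the Prior/Concomitant Medications CRF with their true start dates.

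**What to change.** Replace the concomitant rule in SAP 9.1.1 with: any medication whose stop date is on or after the date of first dose, or which is ongoing, regardless of start date. Leave the prior rule unchanged, and keep PAH drugs under SAP 9.1.2.

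On the same grid this gives 465 prior and 527 + 960 = 1487 concomitant patterns, 1952 in total, with none unclassified and none in both classes.

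The cost is one sentence of SAP text and the matching line of table programming. It needs no new data and changes no treatment rule. If the database is already locked, Protocol 8.5.6 requires the change to be documented in the clinical study report.
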